 - a. We will perform a sensitivity analysis of the impact on antibiotic use outcomes after excluding patients diagnosed with tracheobronchitis within 7 days of index culture. The hypothesis is that the intervention will have limited impact on those diagnosed and treated for ventilator-associated tracheobronchitis, and thus, we may see a larger difference between intervention and control when excluding patients with diagnoses of tracheobronchitisVentilator-free days: Ventilator-free days is defined as the number of calendar days within 28 days after the index respiratory culture on which the patient was not mechanically ventilated. Any patient dying within 28 days of the index respiratory culture collection will be assigned zero ventilator-free days. Ventilator-free days will be compared between the intervention and control periods for all study ICUs combined, and by hospital.
3. Rate of requests for complete reports in the intervention period – these data are applicable in the intervention period only. This will be a primarily descriptive analysis to help us understand if the intervention worked as intended i.e., how frequently did clinicians still want the full report with organism identification despite the nudge to consider asymptomatic colonization.
4. Adverse event outcomes: Death, bacteremia, and septic shock (from any cause) within 7 days of the index culture order will be recorded as potential significant adverse events from a delayed or missed true VAP diagnosis or delay in initiation of appropriate antimicrobial therapy, similar to methods described by Daley et al.¹ Incidence of these events will be compared between intervention and control periods individually for each event, and as a combined adverse event outcome. Two-person adjudication will be used to determine whether the above events were attributed to the intervention, during the intervention period.

Statistical methods for Aim 1:

Descriptive analyses using the Wilcoxon rank-sum test for continuous variables and the chi-square or Fisher’s exact tests for categorical variables will be used to compare patient-level data across each intervention arm. Analyses will be conducted on an intention-to-treat basis and will account for the cluster-randomized crossover design to ensure correct type I error rates and confidence intervals (CIs). A significance level of 0.05 will be used for all statistical comparisons.

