Primary Outcome: The primary efficacy outcome is the reduction in proportion of unnecessary antibiotic therapy for presumed VAP in the intervention period i.e., modified reporting period compared to control period or standard reporting period, among patients not meeting criteria for culture order and with growth of one or more organism(s) not considered normal upper respiratory flora. Antibiotic therapy given for a culture that was collected in a patient not meeting algorithm criteria will be considered unnecessary (dichotomous outcome yes/no). For the primary outcome analysis (and all other patient-level analyses below), a patient will be included once in a given admission and the outcome will be assessed on the basis of a randomly selected qualifying respiratory culture during that admission (termed index respiratory culture). We will estimate the proportion of the primary outcome (i.e., unnecessary antibiotic therapy) in each intervention arm and will compare the two groups using risk difference from a generalized linear mixed model with an identity link function. The main analysis for the primary outcome will be intention-to-treat; a secondary per protocol (as treated) analysis will be done in which any cultures during the intervention period for which a modified report was requested but either the modification was not made, or the report was modified but the full report was released upon provider request or other reason, will not be included in the intervention group.

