Power and Sample Size: For the population of ICU patients for which ordering of a respiratory culture has been determined inappropriate and there is growth of one or more organism(s) not considered normal upper respiratory flora, we test the effect of the diagnostic stewardship intervention on the proportion of antibiotic prescription in a two-period cluster-randomized cross-over design, where an ICU forms a cluster. The outcome follows a binary distribution with 50% probability to receive antibiotic prescription in the control group (pC). In a conservative estimate, we expect that the intervention reduces the probability by $\Delta = 0.15$ (= pC – pI) percentage points. Assuming the within-cluster within-period correlation is $\rho = 0.06$ and the within-cluster between-period correlation is about $\eta = 0.054$ ^{2,3} a total sample size of $N = 350$ in 6 ICUs across both periods is needed to detect an effect of $\Delta = 0.20$ with 85% power, using a generalized linear mixed model with random cluster, period, and cluster-period interaction effect. The computed total N is equivalent to a mean of about 5 patients per ICU per month, which is feasible in our experience. Given the uncertainty in predicting the actual number of patients that will be eligible to receive the intervention per ICU during the fixed 6-month period, we calculated the power for varying range of effect sizes and total N (Table).

Option	Power	Proportion control	Proportion intervention	N patients eligible for intervention per ICU per period*	Within-cluster within-period rho	Within-cluster between-period rho	Total N
1.	90%	50%	35%	30	0.06	0.054	619
2.	85%	50%	35%	30	0.06	0.054	547
3.	80%	50%	35%	30	0.06	0.054	493

4.	90%	50%	30%	30	0.06	0.054	390
5.	85%	50%	30%	30	0.06	0.054	350
6.	80%	50%	30%	30	0.06	0.054	322
7.	90%	50%	25%	30	0.06	0.054	285
8.	85%	50%	25%	30	0.06	0.054	261
9.	80%	50%	25%	30	0.06	0.054	243

Cluster- and participant-level covariates at baseline will be reported within each intervention arm. Adjusted analysis of the primary outcome will be performed as needed to control for differences in possible influential factors between intervention arms at baseline.

Statistical Methods for Secondary outcomes:

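### The primary mixed model rests on 6 ICUs with no small-sample method fixed, so the promised type I error rate and confidence interval are not secured

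*SAP*

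**What the plan says.** In the SAP, the general paragraph under Statistical methods for Aim 1 says that analyses "will account for the cluster-randomized crossover design to ensure correct type I error rates and confidence intervals (CIs", and adds: "A significance level of 0.05 will be used for all statistical comparisons". The Primary Outcome paragraph under the same heading specifies a "risk difference from a generalized linear mixed model with an identity link function".

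Power and Sample Size supplies the random structure, "using a generalized linear mixed model with random cluster, period, and cluster-period interaction effect", and the size: "a total sample size of $N = 350$ in 6 ICUs across both periods" "is needed to detect an effect of $\Delta = 0.20$ with 85% power". The control rate is a "50% probability to receive antibiotic prescription in the control group".

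Statistical Methods for Secondary outcomes applies similar mixed models to antibiotic duration and to adverse events. None of these sections says how the models are estimated, what reference distribution is used, how degrees of freedom are obtained, or whether a small-sample correction applies.

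**The concern.** Six ICUs give six within-ICU differences between periods. After the period effect is removed by comparing the two sequences, 6 − 2 = 4 degrees of freedom remain to estimate the cluster-period variance. With so few, two choices that the SAP leaves open affect the primary result: whether the variance is estimated by maximum likelihood (biased low) or REML, and whether the statistic is referred to a normal or a t distribution. An uncorrected choice can give a confidence interval that is too narrow and a p-value that is too small.

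The method of the primary test belongs in the SAP. If it stays open, it could be settled by a software default, possibly after the data are seen.

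**Working it through.** **Inputs (SAP, Power and Sample Size, unless noted).** 6 ICUs, two periods, N = 350, 50% v 30%, within-period correlation ρ = 0.06, between-period correlation η = 0.054, 30 patients per ICU per period, α = 0.05 (Statistical methods for Aim 1). The SAP does not give sidedness; two-sided is assumed and reproduces the table.

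**Step 1: reproduce the plan's N.**

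Design effect = 1 + (m − 1)ρ − mη = 1 + 29 × 0.06 − 30 × 0.054 = 1.12.

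N = 2(z₀.₉₇₅ + z₀.₈₅)² × [p₁q₁ + p₂q₂]/Δ² × 1.12 = 2 × (1.960 + 1.036)² × (0.25 + 0.21)/0.04 × 1.12 = 231.3.

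This is far from 350. Adding two clusters (2 × 2 periods × 30 = 120 patients) gives 351.3. The same rule reproduces every row to within about 1 patient:

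| Option | Formula | + 120 | SAP |
|---|---|---|---|
| 1 | 499.5 | 619.5 | 619 |
| 2 | 426.8 | 546.8 | 547 |
| 3 | 373.1 | 493.1 | 493 |
| 4 | 270.7 | 390.7 | 390 |
| 5 | 231.3 | 351.3 | 350 |
| 6 | 202.2 | 322.2 | 322 |
| 7 | 164.8 | 284.8 | 285 |
| 8 | 140.8 | 260.8 | 261 |
| 9 | 123.1 | 243.1 | 243 |

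That the 120 is a small-cluster allowance is an inference; the SAP does not describe it.

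**Step 2: power at N = 350, by reference distribution.**

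m = 350/12 = 29.17, so the design effect is 1 + 28.17 × 0.06 − 29.17 × 0.054 = 1.115.

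SE² = 0.46 × 1.115/(6 × 29.17) = 0.00293, SE = 0.0541, noncentrality = 0.20/0.0541 = 3.69.

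- Normal reference: 95.9%
- t on 5 df (no period term): 83.6%
- t on 4 df (fixed period effect): 78.7% by noncentral t; 77.8% when the ICU-level test is simulated with 29 per ICU-period

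For a 15-point effect (50% v 35%), SE² = 0.4775 × 1.115/175 = 0.00304, noncentrality = 2.72, and 4-df power is 54%. For reference, 85% on 4 df at 20 points would need about N = 435 in 6 ICUs.

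**Step 3: type I error, simulated.** Binary data, 50% in both arms, 6 ICUs, 29 per ICU-period, ρ = 0.06, 100,000 runs. The analysis is a balanced normal-theory mixed model. The between-ICU sum of squares is divided by 4 (REML) or 6 (ML), and pooled with the patient-level variance when the cluster-period component is estimated at zero.

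| η | REML, normal | ML, normal | ICU-level t, 4 df |
|---|---|---|---|
| 0.060 (= ρ) | 3.8% | 4.6% | 4.8% |
| 0.054 (plan) | 5.2% | 6.4% | 5.0% |
| 0.048 | 6.1% | 8.0% | 5.0% |
| 0.030 | 8.4% | 11.4% | 5.0% |
| 0 | 10.1% | 14.4% | 5.1% |

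Repeat runs agreed to within about 0.3 points. Values of η other than 0.054 are assumptions used to show the range. The ICU-level test on 4 df stays near 5% throughout.

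**The case against.** The strongest reply is that the SAP never says maximum likelihood, Wald or normal reference. A reader might infer that the primary test's type I error does exceed 5%. The document does not support that: a Kenward-Roger or t-based test would fit its wording and its promise. At the plan's own correlations a REML fit with a normal reference is close to nominal, and at η = ρ both versions fall below 5%. The larger inflations need an η lower than the plan assumes. This stands, and the point is therefore about a method left open.

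A reader might also infer that 85% power fails for any test with a correct error rate. That is not supported either. At the plan's values the REML test with a normal reference has about 92% simulated power at close to 5% error. The 79% belongs to one test that the SAP does not name, and 4 df presupposes a fixed period effect. The SAP's wording can be read as making period random, and 5 df gives 83.6%.

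The table's apparent two-cluster allowance also suggests that the planners had few clusters in mind. But an allowance in N does not control the error rate of the test. Nor does 85% match the normal-reference figure (95.9%) or the 4-df figure (78.7%) at N = 350.

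Finally, the mixed-model correction has a cost. With 29 per ICU-period, patient-level variation makes up 0.94 of 1.114, about 84%, of the variance of an ICU difference. The cluster-period component is then estimated at zero in about half of simulated trials. A Kenward-Roger-type test has about 3.7% error there, by approximation. That is a reason to choose deliberately between the two methods.

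**Conclusion.** The point holds as an unsecured promise. The SAP commits to correct type I error and confidence intervals, yet fixes no small-sample method for a primary model on 6 ICUs. If an uncorrected normal reference were used, type I error would be about 5% to 6.4% at the plan's correlations and about 8% to 11% at η = 0.03. It would be below 5% only if η is close to ρ. The SAP itself gives η only as approximate, and a prespecified primary test should not depend on it.

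The 4-df power figures (79% for 20 points, 54% for 15) assume two-sided α, equal ICU-period sizes and a fixed period effect. The error rates come from a balanced normal-theory approximation, not from fitting the exact model in the SAP.

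**What to change.** Prespecify one small-sample method for the primary p-value and confidence interval:

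- a REML identity-link linear mixed model with Kenward-Roger or Satterthwaite degrees of freedom; or
- an ICU-level crossover difference referred to a t distribution on 4 df.

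State whether period is fixed or random and whether the test is two-sided. Apply a corresponding correction to the secondary mixed models. In Power and Sample Size, describe the apparent 120-patient allowance. If the 4-df test is chosen, give power at N = 350 as about 79% for a 20-point effect and 54% for 15 points, with the assumptions above.

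The cost is SAP wording, a wider confidence interval, some conservatism of the mixed-model option when the cluster-period variance is near zero, and a less favourable stated power. No extra patients are needed.

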Diagnostic Stewardship for Ventilator Associated Pneumonia

Description of Outcomes and Statistical Analysis Plan

NCT05989269

August 11, 2023

Specific Aim 1: In a cluster-randomized crossover trial among 6 ICUs across 3 medical centers, evaluate the impact of a VAP diagnostic stewardship intervention on antibiotic use, VAP diagnoses, and adverse events.

Hypothesis: We expect a reduction in unnecessary antibiotics for VAP and in VAP clinical diagnoses in the intervention vs. control periods across all sites, without an increase in adverse events.

Primary Outcome: The primary efficacy outcome is reduction in proportion of unnecessary antibiotic therapy for presumed VAP in the intervention (modified reporting) period compared to control (standard reporting period), among patients not meeting clinical criteria for pneumonia and with growth of one or more organism(s) not considered normal upper respiratory flora.

Antibiotic action based on index culture result will be classified as follows:

- a) Not on empiric antibiotic(s), new antibiotic started based on index respiratory culture result, completed course for VAP
- b) Not on empiric antibiotic(s), no new antibiotics initiated based on culture result
- c) On empiric antibiotic(s), changed based on index respiratory culture, completed course for VAP
- d) On empiric antibiotic(s), continued without change following index respiratory culture, completed course for VAP
- e) On empiric antibiotic(s), antibiotics discontinued based on culture results
- f) On empiric antibiotics(s), but this therapy was not directed at the results of the index respiratory culture, and was not directed towards VAP

For patients where culturing was deemed inappropriate, antibiotic use in categories a, c, and d will together be considered “unnecessary antibiotic therapy for presumed VAP”

Note: Multiple respiratory cultures from the same patient may be eligible for intervention i.e., modified reporting during the intervention period. However, clinical outcomes linked to an “index respiratory culture” will be assessed using a single randomly selected respiratory culture from each included patient.

Secondary outcomes are as follows:

1. Antibiotic consumption outcomes: The following three outcomes will be measured to understand the impact on antibiotic use in ICU patients

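### The SAP expects a 15-point reduction but sizes the trial (N = 350, 85% power) for 20 points without saying why; at 15 points the 6-ICU trial has about 60% power

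*SAP*

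**What the plan says.** All of this is in the SAP, Power and Sample Size, unless noted.

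- **Expected effect.** With 50% of control patients receiving antibiotics, "In a conservative estimate, we expect that the intervention reduces the probability by" 0.15.
- **Effect used for sizing.** The next sentence says that N = 350 "in 6 ICUs across both periods is needed to detect an effect of" 0.20 with 85% power. Nothing explains the move from 0.15 to 0.20.
- **Accrual.** "The computed total N is equivalent to a mean of about 5 patients per ICU per month", which the SAP calls feasible. Each period lasts 6 months.
- **Number of ICUs.** Specific Aim 1 fixes it: "In a cluster-randomized crossover trial among 6 ICUs across 3 medical centers".
- **Purpose of the table.** It is introduced with "Given the uncertainty in predicting the actual number of patients that will be eligible to receive the intervention per ICU". As shown, the column for eligible patients per ICU per period reads 30 in all nine rows. Total N runs from 243 to 619.
- **15-point rows (50% v 35%).** Total N is 493, 547 and 619 for 80%, 85% and 90% power.

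**The concern.** A plan that calls 15 points its conservative expectation and then sizes for 20 has chosen the optimistic side of its own assumption. Either 0.15 is not the planning value, or 350 is not the sample size that goes with it.

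The table should settle this, but it varies the wrong quantity. The stated uncertainty is patients per ICU, yet that number is held at 30. With 6 ICUs and two periods also fixed, total N could not vary at all. The larger totals therefore imply either more ICUs than the trial has or more patients per ICU than the table allows. No row gives the power of the actual trial at 15 points.

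This is the only power statement for the primary outcome. A reader who takes away 85% power may read a non-significant result as evidence of no effect, although such a result would be fairly likely if the plan's own expectation were true.

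**Working it through.** **Inputs from the SAP.** pC = 0.50; pI = 0.35, 0.30 or 0.25; within-period correlation ρ = 0.06; between-period correlation η = 0.054; m = 30 patients per ICU-period; 6 ICUs; two periods of 6 months; significance level 0.05. I assume a two-sided test, since the SAP does not state sidedness.

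**Step 1: reproduce the table.** For a two-period cluster crossover,

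- n_ind = 2(z₀.₉₇₅ + z_power)² [pC(1−pC) + pI(1−pI)] / Δ²
- DE(m) = 1 + (m−1)ρ − mη, so DE(30) = 1 + 29(0.06) − 30(0.054) = 1.12

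For 20 points at 85% power, n_ind = 206.5 and 206.5 × 1.12 = 231.3, well short of 350. Adding 120 (4m at m = 30) gives 351.3. The SAP does not state this allowance; I infer it because it recovers every row:

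| Power | pI | n_ind × 1.12 + 120 | SAP total N |
|---|---|---|---|
| 90% | 35% | 619.5 | 619 |
| 85% | 35% | 546.8 | 547 |
| 80% | 35% | 493.1 | 493 |
| 90% | 30% | 390.7 | 390 |
| 85% | 30% | 351.3 | 350 |
| 80% | 30% | 322.2 | 322 |
| 90% | 25% | 284.8 | 285 |
| 85% | 25% | 260.8 | 261 |
| 80% | 25% | 243.1 | 243 |

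**Step 2: what 6 ICUs supply.** 6 × 2 × 30 = 360. This agrees with the accrual statement: 350/72 = 4.9 per ICU-month.

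| Total N | ICUs at 30 per period (N/60) | Per ICU-period with 6 ICUs (N/12) | Per ICU-month (N/72) |
|---|---|---|---|
| 493 | 8.2 | 41 | 6.8 |
| 547 | 9.1 | 46 | 7.6 |
| 619 | 10.3 | 52 | 8.6 |

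In whole ICUs, the 15-point rows need 9 to 11. The 20-point row at 90% power (390, or 6.5 ICUs) also exceeds 360.

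**Step 3: power in 6 ICUs.** Power = Φ(Δ/se − 1.96), with se² = 2[pC(1−pC) + pI(1−pI)] DE(N/12) / N_eff. N_eff is N − 120, N − 4m or N according to the allowance. The t version uses a noncentral t on 4 df with N_eff = N.

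Worked case, N = 350 and 15 points: m = 350/12 = 29.2 and DE = 1.115. The variance sum is 0.25 + 0.2275 = 0.4775. With N_eff = 230, se = √(2 × 0.4775 × 1.115 / 230) = 0.068, Δ/se = 2.205, and power = Φ(0.245) = 59.7%.

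| Allowance | 20 points, N = 350 | 15 points, N = 350 | 15 points, N = 360 |
|---|---|---|---|
| Constant 120 | 85.0% | 59.7% | 61% |
| 4m | 85.5% | 60.3% | 61% |
| t on 4 df | 79% | 54.1% | 55% |
| None | 96% | 77.6% | 79% |

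Only the first two rows return the SAP's 85% at 20 points. The last two bound the answer under other treatments of having few clusters.

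**Step 4: can the 15-point rows be read as 6-ICU figures?** If 6 ICUs did recruit 493, 547 or 619, m would rise and DE with it (1.19, 1.21, 1.25). Power would then be 78/82/87% (constant 120), 72/76/80% (4m), 65/69/73% (t on 4 df) or 88/90/93% (none), against the stated 80/85/90%. The two allowances that coincide at m = 30 now differ, so these rows cannot be checked for 6 ICUs until the allowance is named.

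**The case against.** Four points can be made for the plan.

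- **No figure is miscalculated.** This stands. Every row reproduces to within about 1 patient. The fault lies in which effect was used and in what the table holds fixed.
- **The table is not tied to 6 ICUs.** The SAP attaches 6 ICUs only to N = 350, which lies within 360. The 30 may serve only as the cluster-period size behind the design effect, with total N as the output. The asterisk on that column points to a footnote that is not in the text at hand and may qualify it. Also, 360 is derived, not stated. All of this is fair, and it softens the 360 comparison. It does not remove it: the trial is fixed at 6 ICUs, the table is offered to cover uncertainty in patients per ICU, and that column does not vary. Nor would a footnote to that column explain the change from 0.15 to 0.20 in the running text.
- **The shortfall is disclosed.** A reader can see that 15 points needs 493 for 80% power beside a headline of 350. True, but the reader cannot see how far power falls in the trial as designed.
- **The range of 54% to 78% mixes methods.** Its ends do not give 85% at 20 points, so the figure consistent with the table is about 60%. That is right, and it rests on an inferred allowance. The range shows that the conclusion does not hinge on the inference.

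A confidence interval for the risk difference would also guard against misreading a null result. It limits the harm but does not replace a correct power statement.

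**Conclusion.** The concern holds. The planned effect and the sizing effect are not reconciled, and the plan gives no power at its own expected effect for the trial it describes. On the formula that reproduces the table, the chance of missing a true 15-point reduction at N = 350 is about 40% (22% to 46% across the methods shown).

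This rests on two-sided testing, the SAP's own correlations, equal cluster-period sizes, and 30 per ICU-period as shown. The additive 120 is inferred. Without any allowance, power is still below 80% at both 350 and 360. The finding does not make the trial invalid; it is a planning statement that should be corrected.

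**What to change.** 1. Reconcile 0.15 with 0.20. Either justify 20 points as the effect the trial is designed to detect, or state the power at 15 points for 6 ICUs by the method the plan used.
2. Name that method, including the small-sample allowance and the sidedness of the test.
3. Rebuild the table with ICUs fixed at 6 and patients per ICU-period varied, giving power for 15, 20 and 25 points. For 15 points it might look like this, with the 4m allowance and, in brackets, t on 4 df to no allowance:

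| Patients per ICU-period | Total N | DE | Power at 15 points |
|---|---|---|---|
| 20 | 240 | 1.06 | 47% (42–64) |
| 30 | 360 | 1.12 | 61% (55–79) |
| 45 | 540 | 1.21 | 75% (68–90) |
| 60 | 720 | 1.30 | 84% (77–95) |

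The last two rows correspond to 7.5 and 10 patients per ICU-month. They exceed the rate called feasible and are there to show the range, not as a target.

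The cost is SAP wording and one recomputed table. Enrolment, model and test are unchanged. The drawback is a less favourable stated power at 15 points.

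### The power table holds 30 patients per ICU per period in every row, so most of its total sample sizes belong to trials with more or fewer ICUs than the 6 planned

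*SAP*

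**What the plan says.** Specific Aim 1 sets the design: "In a cluster-randomized crossover trial among 6 ICUs across 3 medical centers". Power and Sample Size describes a "two-period cluster-randomized cross-over design, where an ICU forms a cluster", and gives one headline figure: "a total sample size of $N = 350$ in 6 ICUs across both periods is needed" "to detect an effect of $\Delta = 0.20$ with 85% power". It equates this to about 5 patients per ICU per month over a fixed 6-month period.

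The section then says that, since the number of eligible patients per ICU cannot be predicted with confidence, "we calculated the power for varying range of effect sizes and total N (Table"). The table has nine options: 90%, 85% and 80% power for a fall from 50% to 35%, 30% or 25%. Its column "N patients eligible for intervention per ICU per period" reads 30 in every row. Total N reads 619, 547, 493, 390, 350, 322, 285, 261 and 243. There is no column for the number of ICUs.

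**The concern.** Two columns of the table cannot both be true of this trial. If 6 ICUs each contribute 30 patients in each of two periods, total N is fixed, whatever the effect size or power. If total N varies and the ICUs stay at 6, the number per ICU-period must vary with it.

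The distinction affects power. In a cluster-crossover design, extra ICUs add information in proportion, whereas extra patients in the same ICUs also raise the design effect. A table that reaches its totals by adding or removing ICUs does not show what 6 ICUs achieve when accrual differs from plan, which is its stated purpose. Options 1 to 3 are the SAP's only power figures for the 15-point reduction that it offers as a conservative expectation. A reader who sees 30 per ICU-period beside 80% power for that effect would conclude that planned accrual delivers it.

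**Working it through.** **Inputs.** From Power and Sample Size: pC = 0.50; pI = 0.35, 0.30 or 0.25; ρ = 0.06; η = 0.054; m = 30 patients per ICU-period; 6 ICUs; two periods. From Statistical methods for Aim 1: "A significance level of 0.05 will be used for all statistical comparisons". Sidedness and dropout are not stated. Two-sided testing and no dropout are assumed, and they reproduce the table.

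**Step 1: no formula needed.** 6 ICUs × 2 periods × 30 = 360. No row shows 360.

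**Step 2: reproduce the SAP's totals.** Let v = pC(1 − pC) + pI(1 − pI) and Δ = pC − pI.

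- N_ind = 2(1.960 + z_power)² v / Δ²
- D(m) = 1 + (m − 1)ρ − mη, so D(30) = 1 + 1.74 − 1.62 = 1.12
- N = N_ind × D(m) + 4m, where 4m = 120 is two extra ICUs with 30 patients in each of two periods

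Option 1: N_ind = 2 × (1.960 + 1.282)² × 0.4775 / 0.0225 = 446.0; × 1.12 = 499.5; + 120 = 619.5 (SAP: 619). Option 5: 206.5 × 1.12 + 120 = 351.3 (SAP: 350). All nine rows agree to within 1.5 patients. For option 1, versions without the two extra ICUs (unpooled, pooled, one-sided, continuity-corrected) give 407 to 537, well short of 619.

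**Step 3: implied ICUs.** With m fixed at 30, each ICU contributes 60 patients, so the number of ICUs is N/60.

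**Step 4: power with 6 ICUs.** Set m = N/12. The formula then leaves N − 4m = 8m patients after the allowance, and

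power = Φ( Δ √(8m / [2 v D(m)]) − 1.960 ).

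Option 1: m = 51.6, 8m = 412.7, D = 1.2495. The first term is 0.15 × √(412.7 / (2 × 0.4775 × 1.2495)) = 2.789, and Φ(0.830) = 79.7%.

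| Option | Reduction (points) | SAP N | Reproduced N | Implied ICUs | m with 6 ICUs | SAP power | Power, 6 ICUs | N needed, 6 ICUs |
|---|---|---|---|---|---|---|---|---|
| 1 | 15 | 619 | 619.5 | 10.32 | 51.6 | 90% | 79.7% | 945 |
| 2 | 15 | 547 | 546.8 | 9.12 | 45.6 | 85% | 75.8% | 753 |
| 3 | 15 | 493 | 493.1 | 8.22 | 41.1 | 80% | 72.4% | 627 |
| 4 | 20 | 390 | 390.7 | 6.50 | 32.5 | 90% | 88.4% | 417 |
| 5 | 20 | 350 | 351.3 | 5.83 | 29.2 | 85% | 85.5% | 345 |
| 6 | 20 | 322 | 322.2 | 5.37 | 26.8 | 80% | 82.9% | 295 |
| 7 | 25 | 285 | 284.8 | 4.75 | 23.8 | 90% | 94.3% | 234 |
| 8 | 25 | 261 | 260.8 | 4.35 | 21.8 | 85% | 92.6% | 196 |
| 9 | 25 | 243 | 243.1 | 4.05 | 20.3 | 80% | 91.0% | 169 |

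The last column is the smallest N at which the Step 4 power reaches the SAP's stated power.

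**Step 5: the literal 30 per ICU-period (N = 360).** For 15 points, 0.15 × √(240 / (2 × 0.4775 × 1.12)) = 2.247, and Φ(0.287) = 61%. The same step gives 86% for 20 points and 97.5% for 25.

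**Step 6: dependence on the small-cluster correction.** Power at the SAP's N with 6 ICUs, using all 12m patients in place of 8m for the normal and t versions:

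| Reduction (points) | SAP | No correction (normal) | SAP's formula | t on 4 df |
|---|---|---|---|---|
| 15 | 90/85/80% | 93/90/88% | 80/76/72% | 73/69/65% |
| 20 | 90/85/80% | 97/96/95% | 88/85/83% | 82/79/76% |
| 25 | 90/85/80% | 99/99/98% | 94/93/91% | 89/87/85% |

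At N = 360, the 15-point power is 79%, 61% and 55% under the three versions.

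**The case against.** The strongest reply is that the commitment that counts is sound. N = 350 in 6 ICUs is 350/12 = 29.2 per ICU-period and 350/72 = 4.9 per ICU per month, which matches the text, and its power comes out at 85.5%. The other rows are planning alternatives. No estimate, test or enrolment target rests on them, and the SAP plans no interim efficacy analysis. This stands, and it limits the practical damage.

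Second, the SAP does not print its formula. The formula was inferred by matching totals, and reading its 4m term backwards treats 6 ICUs as 4 effective ones, a rough device for power. The size of the error therefore depends on the method, and without any correction the 15-point rows would exceed their stated power. That is a fair warning against treating 80/76/72% as exact. It does not rescue the table: the uncorrected version fails to reproduce the SAP's totals, and a t reference with 4 df makes the 15-point shortfall larger.

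Third, the column of 30s carries an asterisk whose footnote is not visible and may have been lost. It might have called 30 a planning average. No footnote can make 12 × 30 equal 619 or 243.

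Finally, options 4 and 6 are off by only 1.6 and 2.9 points. They are approximate rather than badly wrong.

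**Conclusion.** The concern holds. The table fixes the quantity the SAP calls uncertain and in effect varies the number of ICUs, which the design fixes. That 360 conflicts with every tabulated total needs no modelling assumption. Only option 5 fits 6 ICUs well; options 4 and 6 are close.

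By the method that reproduces the SAP's own totals, power for 15 points is overstated by about 8 to 10 percentage points and power for 25 points is understated by about 4 to 11. At planned accrual, the 15-point reduction has about 61% power. These sizes assume two-sided 0.05, no dropout, equal ICU-period sizes, the stated correlations and the inferred two-ICU allowance. Under other small-cluster corrections they move, as Step 6 shows. The headline claim for 20 points is not in question under the SAP's method.

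**What to change.** Replace the table with one that holds ICUs at 6, makes patients per ICU-period the varying column, sets total N to 12 times that number, and gives power for 15, 20 and 25 points. State the formula, the sidedness and the small-cluster correction beside it. With the Step 4 formula the table would read:

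| Patients per ICU-period | Total N | 15 points | 20 points | 25 points |
|---|---|---|---|---|
| 15 | 180 | 38.1% | 61.4% | 82.2% |
| 20 | 240 | 47.0% | 72.6% | 90.7% |
| 25 | 300 | 54.7% | 80.6% | 95.2% |
| 30 | 360 | 61.3% | 86.3% | 97.5% |
| 40 | 480 | 71.5% | 93.0% | 99.3% |
| 50 | 600 | 78.7% | 96.3% | 99.8% |

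If the sponsor prefers another correction, the layout stays and the percentages change. Remove or correct options 1 to 4 and 6 to 9, and amend the sentence that introduces the table to say that patients per ICU-period is what varies.

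The cost is one table and one sentence. Enrolment, conduct and the primary analysis do not change, but the stated power for the 15-point effect becomes less favourable.
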